## **9.2.2 Study population**

### **9.2.2.1 Study 1245.25**

Study 1245.25 included patients with type 2 diabetes mellitus and increased cardiovascular risk. Detailed eligibility criteria can be found in CTR 1245.25 [[c02695839](#), Section 9.3] and the key criteria are summarised below.

The key inclusion criteria were:

- Age  $\geq 18$  years, diagnosis of T2DM
- Drug-naïve or pretreated with any background therapy
- HbA1c criteria
  - Patients who were drug-naïve: HbA1c of 7 to 10%
  - Patients with background therapy: HbA1c of 7 to 9%
- BMI  $\leq 45$  kg/m^2
- With high cardiovascular risk, defined as  $\geq 1$  of the following criteria
  - History of myocardial infarction (>2 months prior to enrollment)
  - Multi-vessel coronary artery disease:  $\geq 2$  major vessels or left main coronary artery
  - Single-vessel coronary artery disease with no scheduled revascularization/Previously unsuccessful revascularization
  - Hospital discharge due to unstable angina pectoris (>2 months prior to enrollment)
  - History of stroke (>2 months prior to enrollment)
  - Peripheral occlusive arterial disease

The key exclusion criteria were:

- Uncontrolled hyperglycemia: fasting plasma glucose  $>240$  mg/dl
- Severe renal impairment defined as eGFR  $<30$  ml/min by MDRD formula
- Intake of an investigational drug in another trial within 30 days prior to intake of study medication in this trial, or participating in another trial (involving an investigational drug and/or follow-up)

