## **9.5 STUDY SIZE**

This meta-analysis will be based on patients treated with at least 1 dose of study medication (“treated set”) in the 3 studies. Patients are assigned to treatment groups according to randomisation.

Study 1245.25 included 7020 patients treated with empagliflozin 10 mg (N = 2345), empagliflozin 25 mg (N = 2342), or placebo (N = 2333).

Study 1245.110 will randomise approx. 4126 patients to empagliflozin 10 mg or placebo in a 1:1 ratio. Study 1245.121 will randomise approx. 2850 patients to empagliflozin 10 mg or placebo in a 1:1 ratio. Almost all randomised patients are expected to be treated.

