## **9.7 DATA ANALYSIS**

This meta-analysis will be exploratory. For the primary outcome of LLA events and for the secondary outcome of AEs related to amputation, a Cox proportional hazards regression model for modelling the time to first event will be used, including the factors study, diabetes mellitus status (T1DM, T2DM, no diabetes), and treatment (all empa vs. placebo). Study is assumed as fixed effect in this meta-analysis. For treatment comparison, hazard ratios with corresponding 95% CIs as well as corresponding p-values will be presented (see the SAP [[c16853237](#), Section 4.3]).

All analyses will be based on the treated set, which includes all patients treated with at least 1 dose of study medication (as randomised). Due to the different patient eligibility criteria (see [Section 9.2.2](#)) and methods in capturing LLA and related events (see [Section 9.3.2.1](#)), two analysis groupings will be used in the meta-analysis. SAF-M1 includes all 3 studies while SAF-M2 includes studies 1245.110 and 1245.121 (Table 9.7: 1; also see the SAP [[c16853237](#), Table 3.1.2: 1]). All analyses will be carried out separately for each SAF and for each study, unless otherwise indicated in [Table 9.7: 2](#).

Table 9.7: 1 Overview of analysis groupings and individual studies

Grouping	Description	Studies	Purpose
SAF-M1	All studies	1245.25	Frequencies, incidence rates and time to onset of amputation events
		1245.110 1245.121	Frequencies, incidence rates and time to onset for related events based on selected adverse events
SAF-M2	Chronic heart failure studies	1245.110	Frequencies, incidence rates and time to onset of amputation events
		1245.121	Frequencies, incidence rates and time to onset for related events based on selected adverse events
			Details on lower limb amputations

The results of the meta-analysis will be presented mainly in tabular form, and when appropriate, in graphical form.

Tabulations of frequencies for categorical data will include all different categories and display the number of observations and the percentage (%) in a category relative to the respective treatment group (placebo, empa 10 mg, 25 mg, all empa). The category "missing" will be displayed if there are actually missing values. Percentages will be based on all patients in the respective patient set whether they have non-missing values or not.

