### **9.7.1 Main analysis**

LLA events (primary outcome) and AEs related to amputation (secondary outcome) will be analysed using frequency analyses, incidence rates, Kaplan-Meier estimates, and Cox proportional hazards models to compare empagliflozin with placebo in the pooled populations of SAF-M1, SAF-M2, and for each of the 3 studies (1245.25, 1245.110, and 1245.121) separately. Kaplan-Meier analyses (cumulative incidence functions) for time to first event will be provided by treatment and stratified by study.

Cox proportional hazards models will include the factors study, diabetes mellitus status (T1DM, T2DM, no diabetes), and treatment (all empa vs placebo).

As the primary analysis, the “on-treatment” approach will include events with an onset date within the treatment period (from first to last dose of study medication plus 7 days to account for the residual drug effect).

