#### 9.7.2.3 Subgroup analysis

All subgroup variables with categories are shown in [Table 9.3.3: 2](#). Subgroup analyses for SAF-M1 and SAF-M2 will be provided for frequency and incidence rate tables, KM analyses, and for Cox models. Subgroup analyses will be performed for LLA events and AEs related to amputation.

For Cox models for time to first event analysis, the following factors will be included in the model: study, treatment, <subgroup>, treatment-by-<subgroup> interaction.

For time-to-event endpoints, at a minimum, a count of events will be provided, and if sample size is statistically sufficient, i.e. 14 patients with events in total over the 2 treatment groups for each subgroup category, a statistical analysis using the Cox regression model will be performed. If the affected category is too small (<14 patients with events), the category may be only described descriptively and no inferential analysis is performed, or the category may be pooled with another category if this is justifiable from a scientific perspective.

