4.3.2.3 Subgroup analyses

Subgroup analyses will be performed for the subgroups displayed in [Table 4.3: 3](#). Subgroup analyses for SAF-M1 and SAF-M2 will be provided for frequency and incidence rate tables, KM analyses and for Cox models. Subgroup analyses will be performed for amputation events as well as for the adverse events related to amputations analysis.

For Cox models for time to first event analysis the following factors will be included in the model: study, treatment, <subgroup>, treatment by <subgroup> interaction.

For time-to-event endpoints, at a minimum, a count of events will be provided, and if sample size is statistically sufficient, i.e. 14 patients with events in total over the 2 treatment groups for each subgroup category, a statistical analysis using the Cox regression model will be performed. If otherwise the affected category is too small (<14 patients with events) a category may be only described descriptively and no inferential analysis is performed, or the category might be pooled with another category if this is justifiable from a scientific perspective.

Table 4.3: 3 Subgroup analyses

Variable	Subgroup Analysis Categories
Sex	Male Female
Race	White Black/African Asian Other
Geographical region	Europe Africa/Middle East North America Latin America Asia Other (if any)
Age (years) categories	Version 1 < 65 65 to < 75 75 to < 85 ≥ 85 or

	< 65
	65 to < 75
	= 75
	In case of low number of events for patients >= 85
Renal function (eGFR) (CKD-Epi) (mL/min/1.73m ²)	<30 30 to < 45 45 to <60 60 to <90 ≥90
Insulin use	Yes/No (Diabetic patients only)
Metformin use	Yes/No (Diabetic patients only)
SU use	Yes/No (Diabetic patients only)
Loop diuretics	Yes/No
Baseline HbA _{1c} (%)	<8.0, >=8.0
Baseline HbA _{1c} (%)	<8.5, >=8.5
Anticoagulant use	Yes/No
Anti-platelet use	Yes/No
Diuretics	Yes/No
Hypertension	Yes/No
Diabetes	T1DM T2DM No Diabetes (Diabetes yes/no if number of events to low)
Peripheral arterial occlusive disease	Yes/No
Diabetic foot at baseline	Yes/No (Diabetic patients only)
Coronary artery disease	Yes/No
Diabetic neuropathy	Yes/No
Diabetic retinopathy	Yes/No (Diabetic patients only)
History of lower limb amputation	Yes/No
Osteomyelitis	Yes/No
Gangrene	Yes/No
Nephropathy	Yes/No
HF at baseline	Yes/No
Smoking status	current smoker ex-smoker never smoked

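### In SAF-M1 the subgroup Cox models omit diabetes status and force one study contrast on all subgroup levels; with unequal allocation between studies this can bias results for diabetes-related subgroup variables

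*Protocol*

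**What the plan says.** Main model, protocol Section 9.7.1: "Cox proportional hazards models will include the factors study, diabetes mellitus status (T1DM, T2DM, no diabetes), and treatment (all empa vs placebo"). SAP Section 4.3 gives the same factors. On study, protocol Section 9.7 adds: "Study is assumed as fixed effect in this meta-analysis".

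Subgroup model, protocol Section 9.7.2.3: "study, treatment, <subgroup>, treatment-by-<subgroup> interaction". SAP Section 4.3.2.3 lists the same four terms: "study, treatment, <subgroup>, treatment by <subgroup> interaction". Diabetes status has gone, study remains as a main effect, and there is no study-by-subgroup term. The model serves both LLA and AEs related to amputation, in SAF-M1 and SAF-M2.

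Allocation, protocol Section 9.5: 1245.25 treated patients with "empagliflozin 10 mg (N = 2345), empagliflozin 25 mg (N = 2342), or placebo (N = 2333"). For the other two trials: "Study 1245.110 will randomise approx. 4126 patients to empagliflozin 10 mg or placebo in a 1:1 ratio" and "Study 1245.121 will randomise approx. 2850 patients to empagliflozin 10 mg or placebo in a 1:1 ratio".

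Diabetes mix: "Study 1245.25 included patients with type 2 diabetes mellitus and increased cardiovascular risk" (protocol Section 9.2.2.1). The design summary in Section 9.1 describes the heart failure (HF) trials as enrolling patients with and without type 2 diabetes.

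In protocol Table 9.3.3: 2, insulin, metformin, sulphonyl urea, diabetic foot and diabetic retinopathy are limited to diabetic patients. Diabetic neuropathy, nephropathy, renal function and PAOD carry no such limit.

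**The concern.** Treatment is randomised within each study, and study is in the model, so one expects the treatment terms to be protected. In a pooled subgroup model that protection needs the study effect to be right at each subgroup level. Non-diabetic HF patients can be expected to gather in the No level of diabetes-related variables. If they have a lower event rate, the contrast between the HF trials and 1245.25 differs between the No and Yes levels. The planned model has room for only one contrast. Because the share on empagliflozin differs by study, part of the misfit passes into the treatment terms, with opposite signs in the two levels.

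At stake is apparent effect modification by a diabetes-related risk factor that is really an artefact of the allocation ratio. Protocol Section 9.9 relies on subgroup analyses to judge the impact of differences between the trial populations, and diabetes is one of the main differences.

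**Working it through.** **1. Figures from the documents.** 2345 + 2342 + 2333 = 7020, and 7020 + 4126 + 2850 = 13 996, which matches the stated total of about 14 000. In 1245.25 the split is (2345 + 2342):2333 = 4687:2333 = 2.01:1, so 4687/7020 = 66.8% received empagliflozin, against 50% in the HF trials. The documents give no LLA rates and no diabetes share for the HF trials. All such inputs below are assumptions.

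**2. The mechanism by hand, neuropathy-like variable.** Assume that half of HF patients are diabetic, that 30% of diabetic patients (and no others) have the condition, and that the true HR is 1 everywhere. Assumed rates per 100 patient-years are 0.5 in diabetic patients without the condition, 0.5/4 = 0.125 in non-diabetic patients, and 0.5 × 4 = 2.0 in diabetic patients with it.
- No level, HF trials: (0.50 × 0.125 + 0.35 × 0.5)/0.85 = 0.279. In 1245.25 it is 0.5. HF to 1245.25 contrast: 0.56.
- Yes level: 2.0 in both. Contrast: 1.00.

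A single contrast must lie between these. In the No level, 1245.25 then has more events than fitted, and 66.8% of its patients are on empagliflozin, so the HR is pushed above 1. In the Yes level it is pushed below 1.

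**3. Fit.** This is an expected-count Poisson model, the rare-event counterpart of the Cox model:

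log rate = study + β·treatment + γ·subgroup + δ·(treatment × subgroup)

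It gives HR(No) = exp(β) and HR(Yes) = exp(β + δ). Follow-up is 2.6 years in 1245.25 (the stated median) and an assumed 2.0 and 1.4 years in 1245.110 and 1245.121. With z = ln(ratio of HRs)/SE, the true size of a 5% two-sided interaction test is Φ(−1.96 − z) + Φ(−1.96 + z).

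| Scenario (true HR 1) | Events | HR No / Yes | Ratio | Size |
|---|---|---|---|---|
| Central: condition in 40% of diabetic and 20% of non-diabetic HF patients, 30% in 1245.25; hazard ×4 for diabetes, ×2 for condition | 171 | 1.020 / 0.979 | 0.960 | 5.2% |
| Neuropathy-like, as in step 2 | 239 | 1.053 / 0.968 | 0.919 | 6.1% |
| Neuropathy-like, secondary outcome, hazard ×2 for diabetes | 2468 | 1.031 / 0.979 | 0.950 | 9.4% |

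For row 2, SE = 0.273 and z = −0.0845/0.273 = −0.31. For row 3, SE = √(0.065² + 0.054²) = 0.084 and z = −0.0513/0.084 = −0.61. With about 3800 events and hazard ×4 for diabetes, the size is 23%.

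**4. Range.** Using 1.7 years of HF follow-up, 40–50% of HF patients diabetic, LLA rate 3–10 times higher with diabetes, and neuropathy in 30% of diabetic patients at rate ratio 2–4, the HRs are 1.03–1.08 (No) and 0.94–0.97 (Yes), ratio 0.89–0.94. A PAOD-like variable gives about 1.02 and 0.98. Over a wider grid of 6480 settings the ratio runs from 0.73 to 1.19 (5th to 95th percentile 0.84 to 1.05). Test size for LLA has median 5.3%, 95th percentile 8.4% and maximum 20%.

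**5. Check on simulated patient data.** A Cox fit of the neuropathy-like LLA case (350 runs) gives 1.07 / 0.97 and size 6.6% for the planned model. With diabetes status added it gives 1.02 / 1.00 and 5.4%.

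**6. Where the bias vanishes.** The fit returns 1.000 / 1.000 if allocation is equal in all studies, if the variable is unrelated to diabetes within the HF trials, if diabetes itself is the subgroup, or if only diabetic patients are analysed.

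**7. Which term removes it.** Adding diabetes status gives 1.000 in all 6480 settings, but those data were generated from just that multiplicative model. If the PAOD rate ratio is instead allowed to differ between 1245.25 and the HF trials (2 against 4), adding diabetes status moves the HRs only from 1.047 / 0.918 to 1.036 / 0.937. With the two values exchanged it worsens them, from 0.980 / 1.026 to 0.969 / 1.040. Study-by-subgroup terms, or stratification by study and subgroup, give 1.000 in both cases.

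**The case against.** The best defence is that study stays in the model, which removes the plain confounding of treatment with study, and that what remains is minor. Much of this stands. For LLA the SE of the log interaction is about 0.27–0.34, so a shift of a few percent would rarely be noticed. Everything is labelled exploratory. The same subgroup analyses run in SAF-M2, where allocation is 1:1 in both trials, and this provides a partial cross-check. With Cox models allowed from 14 patients with events per category, a sparse model is defensible. The neuropathy example also disappears if that variable was meant to be restricted to diabetic patients like its neighbours in Table 9.3.3: 2, although the table does not say so.

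The defence does not dispose of the point for AEs related to amputation. There the SE shrinks with the number of events while the bias does not.

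A reader might go further and infer that SAF-M1 subgroup results are biased in general. The documents do not support that. Five variables are limited to diabetic patients, and Section 9.3.3 describes HbA1c as applying to patients with diabetes. Nothing in the documents ties sex, race, region or smoking to diabetes within the HF trials.

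**Conclusion.** The point holds in a limited form. The omission is plain in both documents and unexplained. In SAF-M1 it can distort subgroup HRs and interaction tests for variables associated with diabetes within the HF trials and not restricted to diabetic patients. SAF-M2, the diabetes subgroup itself and subgroups limited to diabetic patients are untouched by this mechanism.

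The likely size is a few percent on each HR. That is of little consequence for LLA. It is potentially visible for the secondary outcome if events number in the thousands. These sizes rest on assumed diabetes shares, event rates, prevalences and HF follow-up. Only the patient numbers, the allocation and the 2.6-year median exposure come from the documents. The direction also depends on the inputs, as the grid includes ratios above 1.

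**What to change.** In protocol Section 9.7.2.3 and SAP Section 4.3.2.3:

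- Keep diabetes status in the subgroup Cox model, as in the main model. Collapse it to diabetes yes/no if T1DM is sparse. Omit it where diabetes is the subgroup or only diabetic patients are analysed.
- For SAF-M1, stratify the baseline hazard by study and subgroup level, or add a study-by-subgroup term, so that study contrasts may differ by level. Treatment is then compared within study at each level. This also covers differences that diabetes status cannot, such as the different capture of LLA in 1245.25 described in protocol Section 9.9.
- State in Table 9.3.3: 2 and SAP Table 4.3: 3 whether diabetic neuropathy is restricted to diabetic patients.

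The cost is a few extra parameters or strata, which will be felt in small subgroup models near the 14-event threshold. Diabetes status is already needed for the main analysis, so no new data are required.

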#### 9.7.2.4 Other analysis

Patient disposition, demographics, baseline conditions, exposure, and concomitant diagnoses and therapies will also be summarised based on the treated set. The disposition will show patients randomised and completed, patients who withdrew after randomisation and categorised reason for withdrawal. In addition, a table summarising patients with diabetes and the type of diabetes will be shown. Demographic and baseline variables with categories are shown in [Table 9.3.3: 1](#). Concomitant diagnoses will be summarised by system organ class and preferred term. Relevant diabetic medical history by treatment group will also be presented. Concomitant medications will be summarised by ATC3 and preferred name, for medications taken at baseline and those initiated on randomised treatment. Antidiabetic, antihypertensive, ASA, and lipid-lowering medications will also be summarised.

### **9.7.3 Handling of missing data**

#### **9.7.3.1 Missing amputation date**

In studies 1245.110 and 1245.121, the date and other details on LLA events are to be captured on eCRF pages; therefore, no missing dates are expected. However, LLA events were not specifically captured via eCRF in study 1245.25.

For any missing date of the LLA event, the date is imputed as the date of admission to the hospital or the date of the diagnosis of the event triggering the amputation, whichever is later. In case the date information is incomplete (e.g. only year and month are reported), the mid-point of the possible interval will be used according to BI standard imputation rules for concomitant therapies.

For LLA event, a sensitivity analysis will be conducted for incidence rate calculation in SAF-M1 and SAF-M2 excluding all patients with amputations with missing onset dates. This analysis will only be performed if >10% of onset dates are missing.

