### **9.3.1      Exposures**

Exposure is defined as the time exposed to study medication (on-treatment approach; calculated as the difference between the date of last intake of study medication and the date of the first administration of the study medication plus 1 day) or the time under observation after starting randomised treatment (ITT approach; calculated as the difference between the date of last follow up and the date of the first administration of the study medication plus 1 day; also see SAP [[c16853237](#), Section 4.3.2.1]).

For incidence rate, the derivation of time at risk is as follows:

Patients with event:

time at risk in days = date of start of first event – treatment start date + 1

Patients without event:

time at risk in days = last date on treatment + 7 days\* (or last date in study for secondary analysis based on ITT approach) – treatment start date + 1

\* This is according to the definition of the residual effect period of 7 days as defined in the trial protocols for safety analyses for treatment-emergent events (also see SAP [[c16853237](#), Section 4.3].

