Proprietary confidential information © 2019 Boehringer Ingelheim International GmbH or one or more of its affiliated companies

For continuous variables the set of summary statistics in tables is: N (number of patients with non-missing values) / Mean / SD / Min / Q1 (lower quartile) / Median / Q3 (upper quartile) / Max.

For frequency analyses based on pooled data the estimates for the relative frequency is defined as follows:

$$\hat{p}_j = \frac{\sum_{i=1}^k w_{ji} \cdot \hat{p}_{ji}}{\sum_{i=1}^k w_{ji}}, \text{ where}$$

$\hat{p}_{ji}$  relative frequency in treatment group j and study (i=1,.., k)

$w_{ji} = \frac{n_{ji}}{\sum_i n_{ji}}$  denotes the weight of study i,  $i=1, \dots, k$  in treatment group j

$n_{ji}$  number of patients in treatment group j and study i (i=1, ..k)

The frequency (%) of AEs does not take into account the duration of treatment. This is particularly important when studies with different treatment durations are pooled for analysis. In this case incidence rates may provide more accurate comparisons among groups.

Incidence rate is the number of new cases of an event occurring in a specified time period divided by the cumulative time at risk (see [Section 9.3.1](#) for the derivation).

The incidence rate per 100 patient-years is calculated as follows:

Incidence rate [1/100 pt-yrs] = 100 \* number of patients with event / sum of time at risk over all patients [years].

The estimate for a pooled incidence rate in treatment group j is defined as follows:

$$\hat{IR}_j = \frac{\sum_{i=1}^k w_{ji} \cdot \hat{IR}_{ji}}{\sum_{i=1}^k w_{ji}}, \text{ where}$$

$\hat{IR}_{ji}$  Incidence rate in treatment group j and study (i=1,.., k)

$w_{ji} = \frac{t_{ji}}{\sum_i t_{ji}}$  denotes the weight of study i,  $i=1, \dots, k$  in treatment group j

$w_{ji} = \frac{t_{ji}}{\sum_i t_{ji}}$  denotes the weight of study  $i$ ,  $i=1, \dots, k$  in treatment group  $j$

$t_{ji}$  sum of time at risk in treatment group  $j$  and study  $i$  ( $i=1, \dots, k$ )

Due to the different study designs, not all analyses will be performed for each of the 2 pools. Table 9.7: 2 indicates which safety analyses will be performed for which pool and the individual studies (also see the SAP [[c16853237](#), Table 4.3: 1]).

Table 9.7: 2 Overview of analyses that will be performed for the different study poolings and for the individual study

Endpoint	Poolings and individual study				
	SAF-M1	SAF-M2	Study 1245.25	Study 1245.110	Study 1245.121

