In addition as graphical display a cumulative incidence analysis for amputations and competing event of death will be performed.

The competing risk analysis will be performed according to the standard time to event analysis with censoring at the date of last study medication + 7 days and as additional secondary analysis censored at the date of last follow up.

Trial heterogeneity

In general, some heterogeneity between the studies can be expected due to the different populations involved in the trials to be pooled.

The degree of heterogeneity of the treatment effect between studies will be assessed statistically and clinically/visually.

For time-to-event outcomes, visual inspection of heterogeneity includes a forest plot of the individual study hazard ratios, alongside the corresponding estimate from the individual patient data meta-analysis in SAF-M1 and SAF-M2. For statistical assessment of heterogeneity, a Cox model will be provided including in addition the treatment-by-study interaction term. The p-value of the interaction term from the Cox model in SAF-M1 and SAF-M2 will be used as a statistical measure for heterogeneity.

For binary outcomes (frequencies and incidence rates of LLAs and AEs related to amputation), visual inspection of heterogeneity will be performed using forest plots. These will display the frequencies/incidence rates per treatment arm within each study, alongside the corresponding estimate from the pooled analysis in SAF-M1 and SAF-M2. For statistical assessment of heterogeneity, I^2 will be calculated for the relative risk of an LLA or AEs related to amputation.

If heterogeneity between studies is present, potential sources of variability will be assessed clinically and conclusions outlined in the final report.

Sensitivity analysis for missing dates

For LLA a sensitivity analysis will be conducted for incidence rate calculation in SAF-M1 and SAF-M2 excluding all patients with amputations with missing onset dates. This analysis will only be performed if >10% of onset dates are missing.

Overview of performed analyses

Due to the different study designs not all analyses will be performed for each of the 2 pools. The following table indicates which safety analyses will be performed for which pool and the individually studies.

Table 4.3: 1

Overview of analyses that will be performed for the different study poolings and for the individual study

	Poolings and individual study

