The identification of the confirmed cases of LLA was based on the medical review. Cases included were any amputation/disarticulation of the lower limb, independent of the cause.

The following cases were excluded:

- Amputation/resection/removal of other part of the body than limb (e.g. rectum amputation).
- Amputation of the (part of) upper limb. This is in line with the common medical knowledge that the diabetes mellitus is a risk factor of LLA, not for upper limb.
- Debridement without mentioning of concomitant amputation. It does not include loss of the lower limb segment.
- Necrosectomy without mentioning of concomitant amputation. It does not include loss of the lower limb segment.
- Amputation stump revision without mentioning of an extension of the amputation, and were amputation a preexisting condition at study start.
- Nail removal or resection without mentioning of concomitant amputation. It does not include loss of the lower limb segment.

If the date of the amputation was not properly documented, it was derived by BI based on the available information, i.e. if the date of the procedure was not reported, the date of the admission in the hospital, or the date of the diagnosis for which the amputation was done – whatever occurred later – was used. In one case the day of admission (which was after the date of the diagnosis) was not reported, but only the month and year. It was imputed to 15th in accordance to the imputation done for the CTR.

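### The missing-date sensitivity analysis for amputations drops confirmed cases, so it shows the effect of the deletion and does not test the imputed dates

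*Protocol*

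**What the plan says.** Protocol 9.7.3.1 gives the imputation rule: a missing LLA date is replaced by the later of hospital admission and the diagnosis that led to the amputation. For a partial date it takes the mid-point of the possible interval. For both pools it then plans to recompute the LLA incidence rate "excluding all patients with amputations with missing onset dates. This analysis will only be performed if >10% of onset dates are missing". SAP 4.3 repeats the exclusion: "excluding all patients with amputations with missing onset dates".

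Missing dates are not expected in 1245.110 and 1245.121, which record the date on a dedicated eCRF page. In 1245.25 the cases were found by retrospective search and confirmed by medical review. SAP Appendix 6.2 says of that study: "If the date of the amputation was not properly documented, it was derived by BI based on the available information". It describes one case in which only the month and year of admission were known, and it does not say how many dates were derived in all.

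SAP 4.2 adds that each imputed LLA date will be displayed by study with a narrative justification. No analysis keeps these events and varies their dates. The missing-date check names only the incidence rate, not the Cox or Kaplan-Meier analyses.

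**The concern.** A sensitivity analysis for an imputed date should show how far the result depends on the date chosen. Here the fact of amputation is not in doubt. Removing the patient discards a confirmed primary-outcome event because one attribute of it is uncertain.

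The date enters the on-treatment analysis in two ways. It sets the patient's time at risk, and it decides whether the event falls within last dose + 7 days and so counts at all (Protocol 9.7.1). Deletion examines neither. In a study requested to characterise a possible safety risk, a reader could take a lower amputation rate in the robustness check as information about the dates, when it mostly reflects the removal of cases.

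**Working it through.** The plan gives no figure on this point, so there is nothing to reproduce. The check applies the plan's own rate formula.

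**Inputs from the documents**
- Rate per 100 patient-years: IR = 100 × E / T, with E patients with an event and T total years at risk (Protocol 9.7).
- Time at risk for a patient with an event: "time at risk in days = date of start of first event – treatment start date + 1" (Protocol 9.3.1).
- Data collection in 1245.25: 26 August 2010 to 21 April 2015, at most 4.65 years per patient (Protocol 6).
- Median exposure in 1245.25: 2.6 years (Protocol 9.1).

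**Assumptions, because the documents give no LLA rate or count of missing dates**
- Rate r of 0.2 to 2.0 per 100 patient-years.
- Share m of counted events with a missing date: 10% to 30%.

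**Step 1: direction under exclusion.** Removing k = mE counted events with mean time at risk t gives IR′ = 100(E − k)/(T − kt). This is below IR whenever t < T/E. Since t cannot exceed 4.65 years, the rate falls for any true rate below 100/4.65 = 21.5 per 100 patient-years.

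**Step 2: size under exclusion.** Dividing by IR, T cancels: IR′/IR = (1 − m)/(1 − m × r/100 × t).
- Example: m = 0.10, r = 2, t = 4.65 gives 0.90/(1 − 0.0093) = 0.908, a fall of 9.2%.
- Example: m = 0.30, r = 2, t = 4.65 gives 0.70/(1 − 0.0279) = 0.720, a fall of 28.0%.

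**Step 3: keep the events and move the dates.** Shifting the k dates by s years, with the events staying inside the window, gives IR″/IR = 1/(1 ± m × r/100 × s). Here r runs from 0.5 to 2.
- Example: m = 0.10, r = 2, s = 1 gives 1/1.002, a change of 0.2%.

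| Share missing | Exclusion (r 0.2-2.0) | Dates moved 1 year (r 0.5-2) | Dates moved 2.6 years (r 0.5-2) |
|---|---|---|---|
| 10% | −9.2% to −10.0% | ±0.05% to 0.2% | ±0.13% to 0.52% |
| 20% | −18.5% to −20.0% | not run | not run |
| 30% | −28.0% to −30.0% | ±0.15% to 0.6% | ±0.39% to 1.6% |

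The exclusion column barely depends on t, that is, on when the amputations happened.

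**Step 4: the window.** If an alternative date moves an event outside last dose + 7 days, E falls by one, so the on-treatment rate falls by roughly 1/E for each such event. This is the route by which the date can matter materially, and the planned rule does not look at it. Conversely, a deleted patient whose imputed date already lies off treatment was never in E. Removing that patient takes out person-time only. With the number removed equal to 10% of E and 2.6 years each, the rate rises by 1/(1 − 0.10 × r/100 × 2.6) − 1, which is 0.13% at r = 0.5 and 0.52% at r = 2.

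**The case against.** **Other analyses cover part of the gap.** The ITT analyses count every event in the observation period, on or off treatment, and SAP 4.3 applies them to incidence rates, time-to-event and competing-risk analyses. An amputation placed on the wrong side of the window is still counted there. The individual display in SAP 4.2 lets a reader see each imputed date. Both points stand, so it would be too broad to say that the hazard ratio has no sensitivity analysis; it lacks one specific to missing dates. Neither safeguard shows how the primary on-treatment result moves with the dates.

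**The analysis may never run.** This stands. The number of missing dates is unknown, and none are expected in the heart failure studies. But if the threshold is not reached, imputed dates get no missing-date analysis at all.

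**Deletion resembles an extreme case.** Numerically it comes close to the on-treatment rate that would result if every undated counted event were really off treatment. That is only one end of the range, and it is reached even for patients whose records place the event on treatment. It is not a possible result under ITT, where the window does not apply.

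**Stronger readings that the documents do not support**
- *The check always lowers the rate.* Step 4 shows the exception for events imputed off treatment.
- *At least 10% of cases are deleted whenever it runs.* The threshold counts dates, not patients, and its denominator (study, pool or arm) is undefined. Nor is it stated whether a partial date counts as missing, or whether a dated first LLA with an undated later one leads to exclusion.
- *The check biases the comparison towards empagliflozin.* One might reason that missing dates arise in 1245.25, where 4687 patients received empagliflozin and 2333 placebo. But the planned comparison is the study-adjusted Cox hazard ratio, which the exclusion does not touch, and no rate ratio is listed as an output. Any shift rests on assumed risks and missing shares. With no true effect, LLA in 2% of 1245.25 and 1% of heart failure patients (3488 per arm), and 25% of 1245.25 dates missing, the crude ratio before deletion is (128.62/8175)/(81.54/5821) = 1.12. Deleting 18.2% of empagliflozin and 14.3% of placebo events multiplies it by 0.818/0.857 = 0.954, giving 1.07, which is nearer the true value of 1.

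**Conclusion.** The point holds as a design fault in a conditional, secondary check. For patients counted as on-treatment events, the planned exclusion lowers the LLA rate by almost exactly the share of events deleted, whereas moving the dates within the window changes it by at most about 1.6% even in the most extreme case examined. The result says little about the imputation and leaves the on-treatment window unexamined.

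The sizes rest on assumed rates of 0.2-2 per 100 patient-years for the exclusion and 0.5-2 for the date shifts, and on assumed missing shares of 10-30%. The direction for counted events rests only on the plan's formula, the length of 1245.25 and a rate below 21.5 per 100 patient-years. The point concerns the absolute rates and the missing test of the dates. It does not show a bias in the hazard ratio.

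**What to change.** In Protocol 9.7.3.1 and SAP 4.3, replace the exclusion with an analysis that keeps every confirmed amputee as a case:

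- Recompute the on-treatment incidence rate and the Cox hazard ratio twice, with each imputed LLA date set first to its earliest and then to its latest possible date. Bound both by the documented information and the patient's time in study.
- Reclassify each event as inside or outside last dose + 7 days in each run.
- Run it whenever any LLA date was imputed, in place of the 10% threshold.
- State that partial dates count as imputed, and report the number of imputed dates by study and arm.

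The cost is two extra programme runs and one paragraph in each document. No new data are needed.
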